	Inserting an intra-venous (central or peripheral) or intra-arterial line for research purposes
	Obtaining samples of blood, urine, bone marrow or cerebrospinal fluid for research purposes
	Obtaining a research sample from tissue or organs that would not otherwise be removed during surgery
	Administration of a radio-isotope for research purposes**
	Implantation of an experimental device

Other manipulations or procedures performed solely for research purposes (e.g., experimental liver dialysis, experimental brain stimulation)

If you checked any of the boxes:

You must provide the name and institutional affiliation of a physician anesthesiologist who is a member of your research team or who will serve as a safety consultant about the interactions between your research procedures and the general or regional anesthesia of the subject-patients. If your procedures will be performed at a UW Medicine facility or affiliate, the anesthesiologist must be a UW faculty member.

- ** If you checked the box about radio-isotopes: you are responsible for informing in advance all appropriate clinical personnel (e.g., nurses, technicians, anesthesiologists, surgeons) about the administration and use of the radio-isotope, to ensure that any personal safety issues (e.g., pregnancy) can be appropriately addressed. This is a condition of IRB approval.
- **10.4 Data and Safety Monitoring**. A Data and Safety Monitoring Plan (DSMP) is required for clinical trials (as defined by NIH), and for studies funded by or involving the Department of Justice. If required for your research, upload your DSMP to the **Supporting Documents** SmartForm in **Zipline**. If it is embedded in another document you are uploading (for example, a Study Protocol, use the text box below to name the document that has the DSMP.

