We plan to use a Data Safety and Monitoring Board (DSMB) to review problems when reported, and then in aggregate for this project on an annual basis. These procedures will protect the safety of our research participants and ensure that our study procedures are not harmful in any way. Serious, unexpected adverse events related to mHealth intervention research participation are very rare in studies that are conducted by our group. The PI, in consultation with co-investigators and others as needed, will review Adverse Event reports. They will gather other information to investigate the event and determine the need for subsequent action including reporting to the IRB and if determined an adverse event by the IRB, will then be reported to the DSMB.

10.5 Un-blinding. If this is a double-blinded or single-blinded study in which the participant and/or you do not know the group to which the participant is assigned: describe the circumstances under which unblinding would be necessary, and to whom the un-blinded information would be provided.

N/A

10.6 Withdrawal of participants. If applicable, describe the anticipated circumstances under which participants will be withdrawn from the research without their consent. Also, describe any procedures for orderly withdrawal of a participant, regardless of the reason, including whether it will involve partial withdrawal from procedures and any intervention but continued data collection or long-term follow-up.

Participants will be withdrawn if we find they have previously enrolled in the study, used FOCUS or if they become unavailable for data collection over the 6 month participation (i.e. hospitalized or incarcerated).

10.7 Anticipated direct benefits to participants. If there are any direct research-related benefits that some or all individual participants are likely to experience from taking part in the research, describe them below:

Do not include benefits to society or others, and do not include subject payment (if any). Examples: medical benefits such as laboratory tests (if subjects receive the results); psychological resources made available to participants; training or education that is provided.

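### Protocol 10.4 describes only one route to the DSMB, through a study-team decision and then an IRB determination; events stopped at either step have no stated path to the board

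*Protocol*

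**What the plan says.** Section 10.4 of the Protocol (Data and Safety Monitoring) makes two statements about what reaches the DSMB.

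- **The board's task.** It is "to review problems when reported, and then in aggregate for this project on an annual basis".
- **The route for an event.** "The PI, in consultation with co-investigators and others as needed, will review Adverse Event reports". The same group then investigates and will "determine the need for subsequent action including reporting to the IRB". The sentence ends by saying that the event, "if determined an adverse event by the IRB, will then be reported to the DSMB".

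The section does not say what the annual aggregate contains or whether it is broken down by arm. No other part of the Protocol mentions the DSMB. The SAP does not mention it either, and it describes no safety analysis.

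**The concern.** A monitoring board adds an independent view of safety data. Under the route in 10.4, what it sees depends on two decisions taken before it hears of an event: the investigators' decision to report, and the IRB's classification. The first is not independent of the trial. The second answers a regulatory question about a single event, whereas a board's aggregate review looks for patterns across events and arms.

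Three things are at stake. An event stopped at either step may never be seen by the board. An event that passes both reaches the board only after they are complete, which may not fit a board that reviews problems as they are reported. The annual aggregate could be built from the events that passed rather than from all reported events.

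Relevant events are foreseeable. Section 10.1 says that participants may endorse suicidal ideation during study procedures, and it sets out a staff response. It does not say whether such an episode is handled as an adverse event or reported to the board. Section 10.6 treats hospitalization as a ground for withdrawal, also without a link to event reporting. The supplied documents do not define an adverse event, so both decisions are taken without a written criterion.

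**Working it through.** The plan states no figure on this point, so there is nothing to reproduce. The check is a reading of 10.4, a search for other routes, and a short calculation showing what can and cannot be quantified.

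**1. The steps in order (Protocol 10.4)**

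| Step | Who decides | Condition for going on |
|---|---|---|
| Review of the report | PI with co-investigators | Team judges that IRB reporting is needed |
| Classification | IRB | IRB determines that it is an adverse event |
| Receipt | DSMB | None stated |

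**2. Other routes.** I looked in the rest of the Protocol and in the SAP for a direct feed to the board, a full event listing or counts by arm. There is none. The text says *if* rather than *only if*, but with one route described, the condition works as *only if* for anyone following the document.

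**3. Can the two sentences be read together?** There are three candidate readings.

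- *Reported* means reported to the study. The board then reviews problems as they arise, and the later condition contradicts this.
- *Reported* means reported to the board through the chain. The sentences agree, but the board sees only events that passed both steps.
- Events confirmed by the IRB go to the board one at a time, and the annual review covers all problems. The sentences agree, but the text does not say that the aggregate is compiled this way, and individual review is still restricted.

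Each reading leaves either a contradiction, a restricted view or an unstated step. All three call for the same clarification.

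**4. Share of events seen.** Let *p* be the share of reported events that the team sends to the IRB, and *q* the share of those that the IRB determines to be adverse events. Then

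share reaching the DSMB = *p* × *q*.

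The documents give neither value. Each can lie between 0 and 1, so the share seen can lie anywhere from 0 to 100%.

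**5. Comparison of arms.** If the true event rates in the two arms are *r*₁ and *r*₂, the ratio that the board sees is

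(*p*₁*q*₁ / *p*₂*q*₂) × (*r*₁ / *r*₂).

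Equal pass-through in both arms leaves the ratio unchanged but rests it on fewer events. Unequal pass-through distorts it. The documents give no basis for saying which applies.

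**6. Timing.** The aggregate review is annual, so successive reviews are 12 months apart. Patient participation ends with the 6-month assessment (Protocol 5.1). Suppose an event is not sent to the board individually and does enter the aggregate. The board could first see it up to 12 months later, twice the length of one patient's participation. No interval is given for the team's review or the IRB determination, so the delay for events that do pass cannot be computed.

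**The case against.** **The annual review may be complete.** The text never says what the aggregate contains, and the words *problems* and *adverse event* are different and undefined. A reader might infer that the annual review certainly works from a filtered count and that the board cannot compare arms on all events. The documents do not support either as fact. They support the weaker statement that the aggregate may omit events, because its content is unstated and the only described feed is conditional.

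**A fuller plan may exist.** Section 10.4 is a text box on an IRB form. The form asks for a data and safety monitoring plan to be uploaded, or for the document containing it to be named. None was among the supplied documents, and the answer names none. Neither its existence nor its absence can be asserted, which is why the fix allows for a citation.

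**Materiality is low.** Both arms use the same app and differ in who facilitates it. Section 10.1 describes the risks as minimal and says that no adverse events were reported in earlier deployments of FOCUS. Section 10.4 calls serious, unexpected events related to participation very rare in the group's studies. This stands and limits the severity. It does not reconcile the two sentences.

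**Patients are not left without a response.** Disclosed intent to harm is handled by research staff, the lead investigator and the clinical team under 10.1. The delay concerns board oversight only. It would also be too strong to say that patients are expected to endorse suicidal ideation; 10.1 says that they may.

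**Two further inferences should be resisted.** One is a worked example with assumed event counts in each arm, to show a signal being lost. The counts and the pass-through share would both be invented. A simple test on 300 patients would also ignore that 20 clinics, with 15 patients each, are the unit of randomization. The other is that events would be forwarded differently by arm, because the external facilitators are university staff and the lead researcher is on that university's faculty. The documents show the affiliations, but nothing on how events would be forwarded.

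**Conclusion.** The concern holds as a defect in the reporting route. As Protocol 10.4 is written, events stopped by the study team or by the IRB determination have no stated path to the DSMB, those that pass may arrive late, and the annual aggregate may leave some out. This sits badly with a board meant to review problems when reported.

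The effect cannot be sized, since the share of events seen is unknown and could be anything from none to all. The conclusion rests on two assumptions: that 10.4 is followed as written, and that no separate monitoring plan gives the board another route. Given the minimal-risk description, it is a desirable correction and does not threaten the trial's main results.

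**What to change.** In Protocol 10.4:

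1. Remove the IRB determination as a condition for reporting to the DSMB, so that the section no longer says two different things.
2. State that adverse events reported to the study team go to the DSMB with study arm, whatever the IRB determines.
3. State that the annual aggregate covers all of these events.
4. If a separate data and safety monitoring plan already provides for this, cite it in 10.4 and bring the wording into line.

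When making the edit, it would help to add the definition of an adverse event that the team will use, since the supplied documents give none.

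The cost is a few sentences in the monitoring text and slightly more paperwork for the board. Treatment, sample size and planned analyses are unaffected.

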Randomization will occur at the level of the clinic and will be balanced within study arm by number of patients served and rural/urban designation. Study sites (k=20) will vary in staffing and services capacity. Sites will either be randomized to have an internal facilitator (IF) or external facilitator (EF). The internal and external facilitators will work to engage participating organizations, practitioners, and patients throughout the study which includes sending email and placing phone calls with participating organizations, practitioners and patients in order to conduct the study (i.e., schedule appointments, request materials, etc.). They will provide updates about study progress and will maintain and request data from the study sites.

Patient Participants

After consenting into the study, patient participants will receive a phone call prior to each assessment (OM, 3M, 6M) letting them know they will receive a text or email (for those who have identified trouble receiving text messages) with the assessment URL and to provide instructions for how to complete the assessment (ensure they are in a private place, have reliable data for transmission, will take aprox. 20-30 minutes to complete, etc). Participants will then receive the web-based baseline assessment via text and will be asked to complete it in a private and quiet space. For those who have expressed difficulty completing the assessment through the web-based assessment, a phone call can be conducted with trained assessor to ask questions directly over the phone. Afterward, they will be asked to meet with their assigned facilitator (IF/EF) to install the FOCUS app on their phone, describe how to use it and set up a time for their weekly calls. This may be done via phone call, or video call, whichever is preferred by the participant. Participants will continue to use the program for 3 months in their own environments, along with participating in weekly calls to discuss what they've learned in the FOCUS app and how those strategies can help support their symptom coping strategies.

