The FOCUS application uninstalls at 3 months and then the 3 month web-based outcome assessment will be sent via text and will ask participants to complete it in a private and quiet space. Once again those who express difficulty completing the assessment through the web-based platform can request a call with an assessor on the research team. Participants who complete treatment will be mailed out a certificate of completion to their home address or clinic (based on participant's choice). They will no longer have access to the app, nor will participate in weekly calls for the next 3 months. They would then be sent another assessment at 6 months to complete.

Patient Participant Assessment:

Patient participants will receive a text from researchers just before their assessment date providing instructions on how to complete the online assessment. They will then be invited to conduct assessments at 0, 3, and 6 months via embedded link to a secure study portal (Qualtrics). For participants who need additional assistance, they can come into the participating clinic to complete on a tablet provided by the research team. Patient participants will receive \$30 compensation for each completed assessment (estimated completion time < 45 minutes) for a maximum of \$90 compensation (Plus additional \$10 each assessment to compensate data transmission or travel to site if more assistance is necessary). All participants will be paid for each assessment, but they will not be compensated for engagement in the intervention; assessments are administered to everyone enrolled in the study regardless of how/whether they engaged in FOCUS (note: all patient participants own working smartphones as part of inclusion criteria).

Assessments include questions about psychiatric treatment and hospitalizations, along with other measures of mental health including depression, anxiety, hearing voices, and recovery:

- Demographics and other characteristics
- PhQ9
- GAD-7
- Hospitalization- days hospitalized, no identifiers will be captured.
- ISI: Insomnia Severity Index
- Green Paranoid Thoughts Scale
- Symptom Checklist SCL-9Hamilton Program for Schizophrenia Voices Questionnaire (HPSVQ)
- Recovery Assessment Scale (RAS)
- Illness Management Recovery Scale (IMRS)
- Working Alliance Inventory (3M only)
- mHealth Mastery Measure (3M only)
- AIM
- Satisfaction

Information we plan to collect from EMR data:

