- **d.** Consent. Will you obtain consent now from subjects for the banking and/or future sharing?

Yes → If yes, be sure to include the information about this consent process in the consent form (if there is one) and in your answers to the consent questions in Section 6.

e. Withdrawal. Will subjects be able to withdraw their data/specimens from banking or sharing?

→ If yes, describe how, and whether there are any limitations on withdrawal.

Example: data can be withdrawn from the repository but cannot be retrieved after they are released.

f. Agreements for sharing or release. Confirm by checking the box that you will comply with UW (and, if applicable, UW Medicine) policies that require a formal agreement between you and the recipient for release of data or specimens to individuals or entities other than federal databases.

Data Use Agreements or Gatekeeping forms are used for data; Material Transfer Agreements are used for specimens (or specimens plus data. Do not attach your template agreement forms; the IRB neither reviews nor approves them

x Confirmed

5.9 Communication with subjects during the study. Describe the types of communication (if any) you will have with already-enrolled subjects during the study. Provide a description instead of the actual materials themselves.

Examples: email, texts, phone, or letter reminders about appointments or about returning study materials such as a questionnaire; requests to confirm contact information.

If technical issues are identified or if participants have gone 'dark' (missing data over a period of time) we will provide a text message or call checking in with the participant. Based on their response (i.e. express needing technical support, or non-response), an RA will contact the participant to ensure their phone is working and to assess if they are still interested in participating. If a participant has gone dark for in extended period of time and are unable to be reached by phone, a letter will be sent to their mailing address (email or physical mailing address: copy of letter attached). PHI will not be transmitted in text messages or emails.

5.10 Future contact with subjects. Do you plan to retain contact information for your subjects so that they can be contacted in the future?

No x Yes

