## UNIVERSITY of WASHINGTON

appropriately estimate multilevel regression models and to conduct Monte Carlo simulations. Our multilevel models in MPlus will allow us to accommodate likelihood-based ignorable analyses to obtain unbiased model inference without directly modeling drop-out associated with attrition.

Power Analysis. The sample size for the project is limited by the maximum number of organizations and clinicians that can be recruited within the logistical and financial constraints of an R01. With our available resources, we expect to enroll 20 CMHCs, with 5 clinicians per CMHC, and 3 patients per provider (n=300 patients, 100 providers). Based on our prior work (see Pilot Study B), we were able to calculate a between-organization ICC of 0.19 and a between-patient ICC of 0.45 for patientlevel outcomes similar to those being tested in this study. With an average of 15 patients per site, we will have 80% power to detect small to moderate effects of the implementation strategy on patient outcomes (Cohen's d=0.44). For provider-level outcomes, assuming a between-provider ICC of 0.30, we will have power to detect moderate effects of the implementation strategy (Cohen's d=0.55). Alpha is set at .05 (two-tailed) and will not be adjusted for multiple comparisons because we prefer to explore leads that may turn out to be wrong rather than miss potentially important findings. Using similar model assumptions, the study will have sufficient power to detect moderate effects of organizational-level moderators on patient outcomes (Cohen's d=0.50) and provider outcomes (Cohen's d=0.61). For the mediation analysis, the proposed sample size will yield sufficient power to detect a large indirect effect (Cohen's d=0.85) of the strategy through the practitioner-level mediators and a large indirect effect (Cohen's d=0.65) of the strategy through the patient-level mediators, assuming there is a moderate effect of the implementation strategy.

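### Withdrawing participants who become hospitalized may lose outcome data for symptom-related reasons; the plan does not say whether assessment resumes, and the SAP does not test its missing-data assumption

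*Protocol*

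**What the plan says.** The form question at protocol section 10.6 asks how withdrawal will work, "including whether it will involve partial withdrawal from procedures and any intervention but continued data collection or long-term follow-up". The answer lists only circumstances. One is that participants are withdrawn "if they become unavailable for data collection over the 6 month participation (i.e. hospitalized or incarcerated". It does not separate leaving the intervention from leaving assessment, and it neither provides for nor rules out a later assessment.

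Protocol section 5.1 says that "assessments are administered to everyone enrolled in the study regardless of how/whether they engaged in FOCUS". Its list of patient measures includes "Hospitalization- days hospitalized, no identifiers will be captured". Patients are assessed at 0, 3 and 6 months by web link. For those who have difficulty, "a phone call can be conducted with trained assessor to ask questions directly over the phone", or "they can come into the participating clinic to complete on a tablet provided by the research team". Under section 5.9, when a participant goes silent, "an RA will contact the participant to ensure their phone is working and to assess if they are still interested in participating".

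The only missing-data statement in the SAP, at the end of the Analytic Approach, is that the multilevel models will "allow us to accommodate likelihood-based ignorable analyses to obtain unbiased model inference without directly modeling drop-out associated with attrition". No sensitivity analysis for missing outcomes is named. The only scenarios in the SAP concern the price of FOCUS.

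**The concern.** A likelihood-based analysis that ignores the dropout process is valid when, given the modelled variables and the scores already observed, missingness does not depend on the unseen scores. Withdrawal on hospitalization puts that condition in doubt. The protocol's background (section 1.8a) describes psychiatric hospitalization as a frequent result of symptom worsening, and symptom severity is an Aim 3 outcome. With scores three months apart, the worsening that leads to an admission will often fall between visits and go unrecorded.

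Aim 3 compares patient outcomes between internal and external facilitation, so what matters is bias in the arm contrast. That contrast can be biased if withdrawal depends on unseen scores and, in addition, either the withdrawal rate or the strength of the dependence differs by arm. Outcomes that are never collected cannot be recovered at analysis.

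**Working it through.** The plan gives no figure on this point to reproduce, and no admission or withdrawal rate for this trial. The only dropout figure is 3.5%, in the FOCUS arm of an earlier trial (protocol section 1.8b). All rates, stay lengths and slopes below are assumptions.

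**Two readings of 10.6.**
- Broad: any admission during the 6 months leads to withdrawal.
- Narrow: only someone who cannot be reached at an assessment is withdrawn.

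**Patients affected, if 10% of 300 are admitted.**
- Broad: 0.10 × 300 = 30.
- Narrow: the share in hospital on one of two assessment days is about 2 × stay / 182. For stays of 7, 14 and 28 days this is 7.7%, 15.4% and 30.8%, or 2.3, 4.6 and 9.2 of the 30. With 14-day stays, admission rates of 10% vs 5% become withdrawal rates of about 1.5% vs 0.8%.

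**Bias in the arm contrast.** The simulation used a three-level random-intercept model (visits within patients within sites, arm by visit). The contrast was the arm difference in change from baseline to 6 months.
- Variances: the SAP's Power Analysis gives ICCs of 0.19 (organization) and 0.45 (patient). If 0.45 excludes the site part, the residual is 1 − 0.19 − 0.45 = 0.36. If it includes it, the patient part is 0.45 − 0.19 = 0.26 and the residual is 0.55. Both were run.
- Withdrawal: logistic in the unseen next score, slope 0.7, 1.5 or 3.0 per SD, half the risk at each of 3 and 6 months.
- Bias: the estimate with missing data minus the estimate from the same data complete. Unless noted, the slope is the same in both arms.

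| Assumed withdrawal | Bias in SD |
|---|---|
| 1.5% vs 0.8% (narrow, 14-day stays) | 0.001 to 0.007 |
| 10% vs 5% | 0.012 to 0.036 |
| 20% vs 10% | 0.024 to 0.069 |
| Equal rates, same dependence in both arms | at most 0.003 |
| Dependence on observed scores only | at most 0.001 |
| 10% in both arms, dependence (slope 1.5 or 3) in one arm only | about 0.04 to 0.08 |

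When rates differ, the bias favours the arm with more withdrawals. Independent reruns with simpler fitting gave matching values for 10% vs 5% (0.009 to 0.035 across reruns). In the last row, a shallower slope gives less.

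**Scale.** With 150 patients per arm and no site-by-time variance, the standard error of the contrast is √(4 × residual / 150). That is √(4 × 0.36 / 150) = 0.098 or √(4 × 0.55 / 150) = 0.121 SD. At 10% vs 5% the largest bias is 0.036 / 0.121 ≈ 0.29 of a standard error. For dependence in one arm only, the largest is 0.08 / 0.121 ≈ 0.66.

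**Effect of continued assessment at 10% vs 5%.** If later visits resume but the affected visit is never collected, the bias is 0.009 to 0.031 SD. If the affected visit is collected late in 50% of cases it is 0.004 to 0.014, and in 80% of cases 0.002 to 0.005. This treats the late score as equal to the missed one, which is optimistic.

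**The case against.** The strongest reply is that 10.6 is about being unavailable for data collection and that hospitalization only illustrates this. Section 5.1 records days in hospital, so patients who are admitted and discharged seem expected to remain assessable. On that reading about 5 of 300 patients are affected (10% admitted, 14-day stays) and the bias is negligible. This is a fair reading and limits the size of the point. It does not remove it: the form's question about continued data collection is unanswered, and staff at 20 sites could apply the rule either way. The detailed printed protocols mentioned in section 12.2 may settle it. They are not among the documents, and if they do, a line confirming it would be enough on the protocol side.

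Stronger readings are tempting, and the documents do not support them.
- A reader might infer that every admission triggers withdrawal, or that scores taken before withdrawal are discarded. Neither is stated.
- A reader might infer that internal facilitators, who may have access to patient records, would notice more admissions and so withdraw more people. Section 1.8a offers that access only as a possible benefit. Assessments are sent by researchers in both arms, weekly calls take place in both arms, and re-contact is done by the research team. Nothing says that facilitators decide or report withdrawals.
- A reader might infer that section 5.1 already guarantees assessment after withdrawal. Its sentence concerns people who do not engage with FOCUS.

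Conversely, equal withdrawal rates would not by themselves make the contrast safe, as the last row of the table shows.

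It can also be said that calling the analysis ignorable already names the assumption. It does, but the SAP states the result as unbiased without spelling out the condition or testing it.

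**Conclusion.** The point holds as a cheap improvement. The plan contains a withdrawal rule that is plausibly related to outcome, leaves continued assessment unstated, and pairs this with an untested missing-data assumption. It does not show that the result will be biased.

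The risk is modest: about 0.01 to 0.04 SD at 10% vs 5% withdrawn, under 0.01 SD at 1.5% vs 0.8% on the narrow reading, and about 0.04 to 0.08 SD at 10% in both arms if moderate or steep dependence exists in one arm only. It is close to zero if withdrawal depends only on observed scores, or if both rate and dependence are equal across arms. These sizes rest on assumed rates, stay lengths and slopes, so the actual bias cannot be computed from the documents.

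**What to change.** **Protocol.** Reconcile sections 10.6 and 5.1. For outcome data only, state that a participant who has been hospitalized stays in assessment and is sent the remaining 3- and 6-month assessments once reachable, by the existing web, phone or clinic-tablet routes. The section 5.9 contact steps can be used. Record the actual assessment date. Leave incarceration to the IRB's prisoner provisions (the answer to question 2.3b is not legible in the text available). Nothing here concerns app use or calls.

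**SAP.**
1. State that inference is unbiased only if data are missing at random given the modelled variables and observed scores.
2. Tabulate withdrawals by recorded reason and arm.
3. Add one delta-adjusted sensitivity analysis for Aim 3, for example worsening shifts of 0.25, 0.5 and 0.75 SD, applied in both arms and then in each arm alone, and report the shift at which the conclusion changes.

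Apply the shifts to all scores missing after withdrawal, by recorded reason where known. Limiting them to scores missing after an admission would not work well: days in hospital come from the patient assessment itself, and billing data arrive without identifiers. For scale, a 0.5 SD shift in both arms at 10% vs 5% missing moves the 6-month contrast by 0.5 × (0.10 − 0.05) = 0.025 SD, and in the 10% arm alone by 0.5 × 0.10 = 0.05 SD. At 1.5% missing, even a 0.75 SD shift in one arm moves it by only 0.75 × 0.015 ≈ 0.01 SD. The analysis cannot prove missing at random; it shows how far the conclusion depends on it.

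**Cost.** One short protocol modification, a few SAP sentences, one extra analysis and a little more follow-up work. Payment per assessment is already planned. Some assessments will be late, and a score after discharge may differ from the one missed.
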